11.4. Pharmacokinetic/Pharmacodynamic Analyses

The PK/PD relationship of JNJ-63623872 exposure (AUC_{12h} , C_{max} , or C_{min}) with efficacy (ie, change in viral load from baseline and virologic response) and safety (including AEs and laboratory abnormalities) will be explored. Other exploratory analyses may be performed.

11.5. Safety Analyses

All safety endpoints will be evaluated on the Safety population, consisting of all subjects who received at least one dose of study drug and will be analyzed by drug received. Safety will be evaluated by means of AEs (including complications of influenza), clinical laboratory tests, ECGs, vital signs, NEWS, physical examinations, pregnancy testing, and specific toxicities. The safety analysis will be done for the Safety population and for each study phase separately (treatment, follow-up, and the combination of both).

Adverse Events

The verbatim terms used in the eCRF by investigators to identify AEs will be coded using the Medical Dictionary for Regulatory Activities (MedDRA). Treatment-emergent AEs are AEs with onset during the treatment phase or that are a consequence of a pre-existing condition that has worsened since baseline. All reported AEs will be included in the analysis. For each AE, the percentage of subjects who experience at least 1 occurrence of the given event will be summarized by treatment arm. In addition, comparisons between treatment arms will be provided if appropriate.

Summaries, listings, datasets, or subject narratives may be provided, as appropriate, for those subjects who die, who discontinue treatment due to an AE, or who experience a severe or a serious AE.

Clinical Laboratory Tests

Laboratory data will be summarized by type of laboratory test. Reference ranges and markedly abnormal results (specified in the Statistical Analysis Plan) will be used in the summary of laboratory data. Descriptive statistics will be calculated for each laboratory analyte at baseline and for observed values and changes from baseline at each scheduled time point. Changes from baseline results will be presented in pre- vs. post-treatment cross-tabulations (with classes for below, within, and above normal ranges). Frequency tabulations of the abnormalities will be made. A listing of subjects with any laboratory results outside the reference ranges will be provided. A listing of subjects with any markedly abnormal laboratory results will also be provided.

The laboratory abnormalities will be determined according to the criteria specified in the WHO grading table (see [Attachment 1](#)) and in accordance with the normal ranges of the clinical laboratory if no gradings are available. Laboratory abnormalities will be tabulated by scheduled time point.

Electrocardiogram

The effects on cardiovascular variables will be evaluated by means of descriptive statistics and frequency tabulations. These tables will include observed values and changes from baseline values (the predose ECG will be used as baseline) to allow detection of clinically relevant changes in individuals.

Electrocardiogram data will be summarized by ECG parameter. Descriptive statistics will be calculated at baseline and for observed values and changes from baseline at each scheduled time point. Frequency tabulations of the abnormalities will be made.

The ECG variables that will be analyzed are heart rate, PR interval, QRS interval, QT interval, and QTc interval using the following correction methods: QTcB, QTcF, and QT correction derived by linear regression (QTcL).^{5,9}

Descriptive statistics of QTc intervals and changes from baseline will be summarized at each scheduled time point. The percentage of subjects with QTc interval >450 milliseconds, >480 milliseconds, or >500 milliseconds will be summarized, as will the percentage of subjects with QTc interval increases from baseline >30 milliseconds or >60 milliseconds.

All important abnormalities in ECG waveform that are changes from the baseline readings will be reported (eg, changes in T-wave morphology or the occurrence of U-waves).

The percentage of subjects with abnormalities will be tabulated by treatment arm.

Vital Signs

Descriptive statistics of temperature, pulse/heart rate, respiratory rate, blood pressure (systolic and diastolic) (supine), arterial oxygen saturation values, level of consciousness, and changes from baseline will be summarized at each scheduled time point. For oxygen saturation an overview will be presented for the number of subjects that require supplemental oxygen. The percentage of subjects with values beyond clinically important limits will be summarized. For each subject, the NEWS will be derived based on the vital sign data. The average of the NEWS over time will be presented by treatment group.

Electrocardiogram data will be summarized by vital sign parameters (temperature, pulse/heart rate and blood pressure [systolic and diastolic]). Descriptive statistics will be calculated at baseline and for observed values and changes from baseline at each scheduled time point. Frequency tabulations of the abnormalities will be made.

Physical Examination

Descriptive statistics of changes from baseline will be summarized at each scheduled time point.

Physical examination findings will be summarized at each scheduled time point. Descriptive statistics will be calculated at baseline and for observed values and changes from baseline at each scheduled time point.

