*On room air to be obtained from “Was oxygen saturation measured on room air?” on Vital Signs pages (SUPPVS.QVAL for SUPPVS.QNAM = ‘VSOXSMRA’)

▪ **Time to improvement of respiratory status**

Time to improvement of respiratory status is defined as the time (in hours) from first study treatment until the first assessment (actual date and time) of a successive series of 3 recordings (over 4 scheduled successive analysis time points, 1 missing time point is allowed) where normalization of blood oxygen saturation and respiration rate occurred (as defined in Table 6). Analysis performed will be analogous to the analysis for the time to improvement of vital signs. Note that the NEW Score at baseline should not be added as covariate in the models.

▪ **Clinical outcome on day 8**

The ordinal scale consists of 6 categories that are exhaustive, mutually exclusive, and ordered (Table 7). For all patients, the category at days 1 to 15 will be established as the worst category on that day. The clinical outcome on day 8 will be further analyzed.

The analysis of the clinical outcome on day 8 will be performed using a proportional odds model, modeling the common odds ratio of the improvement on the ordinal scale of active treatment versus control. Age category (≥ 18 - < 65 years, ≥ 65 - ≤ 85 years) and baseline clinical outcome category will be added to the model. In case the model will not fit, age category and subsequently baseline category will be deleted.

In case of missing data ($>10\%$), multiple imputation under the missing-at-random assumption will be employed as a sensitivity analysis. The Markov chain Monte Carlo (MCMC) method will be used to create a number of multiple imputation datasets with monotone missingness in the clinical outcomes (baseline until day 15). The number of imputation datasets will be the same as the percentage of missing data (White *et al.* 2011). A monotone ordinal logistic regression imputation model will be used to complete the remaining missing clinical outcomes. The models fitted using the multiple imputation datasets will be the same as the final model on the actual data. The results from the models on the multiple imputation datasets will be combined taking into account the between and within variation of the results.

Additionally a Wilcoxon–Mann–Whitney test will be performed to compare the clinical outcome on day 8 between the two treatments.

Table 7: Ordinal scale on Day 8

Outcome
Death

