The number and percentage of subjects will be shown in a cross-tabulation of the toxicity/abnormality post-baseline versus baseline at each scheduled time point.

Additionally, a cross-tabulation of the worst toxicity/abnormality versus baseline will be presented per phase (Treatment phase, Follow-up phase) and for the combination of Treatment and follow-up phase. This table will also show the number and percentage of subjects per worst toxicity/abnormality, the number and percentage of subjects per treatment-emergent worst toxicity/abnormality, and the cumulative number of subjects per treatment-emergent toxicity/abnormality or worse.

Mean \pm SE graphs over time for the actual values and changes from reference will be generated for all tests performed.

A tabulation of the worst QT/QTc change versus baseline per treatment per phase will be presented.

Abnormal individual subject ECG values or abnormalities on the changes will be listed.

4.3.4. *Vital Signs*

Systolic and Diastolic blood pressure, oral temperature, pulse rate, respiratory rate, arterial oxygen saturation and level of consciousness will be investigated.

Vital Signs abnormalities will be determined according to the WHO grading scale and the boundaries defined in Appendix 3.

Worst toxicities are determined over the whole observational period for each trial phase separately, including all post-reference scheduled and unscheduled measurements of that phase.

Actual values and change from baseline will be summarized by treatment group at each scheduled time point. A toxicity will be considered treatment-emergent in a particular phase if it is worse than the reference corresponding to this phase. If the reference is missing, the abnormality is always considered as treatment-emergent.

The number and percentage of subjects will be shown in a cross-tabulation of the toxicity/abnormality post-baseline versus baseline at each scheduled time point.

Additionally, a cross-tabulation of the worst toxicity/abnormality versus baseline will be presented per phase (Treatment phase, Follow-up phase) and for the combination of Treatment and follow-up phase. This table will also show the number and percentage of subjects per worst toxicity/abnormality, the number and percentage of subjects per treatment-emergent worst toxicity/abnormality, and the

63623872FLZ2002 Statistical Analysis Plan

cumulative number of subjects per treatment-emergent toxicity/abnormality or worse.

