Mean \pm SE graphs over time for the actual values and changes from reference will be generated for all tests performed.

A listing of abnormal individual subject VS values will be provided.

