Appendix 3 WHO grading scale Vital Signs

The following abnormalities are defined for vital signs:

Abnormality Code	Vital Signs parameter		
	Pulse	DBP*	SBP*
Abnormalities on actual values			
Abnormally low	< 45 bpm	≤ 50 mmHg	≤ 90 mmHg
Grade 1 or mild	-	> 90 mmHg - < 100 mmHg	> 140 mmHg - < 160 mmHg
Grade 2 or moderate	-	≥ 100 mmHg - < 110 mmHg	≥ 160 mmHg - < 180 mmHg
Grade 3 or severe	-	≥ 110 mmHg	≥ 180 mmHg
Abnormally high	≥ 120 bpm	-	-

* The classification of AEs related to hypotension and hypertension will be done according to the WHO grading scale

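### Oxygen saturation is summarised without regard to whether the subject was on oxygen, and the SAP sets no abnormality limit for saturation or respiratory rate

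*Protocol*

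**What the plan says.** Protocol 11.5 (Vital Signs) states that "arterial oxygen saturation values, level of consciousness, and changes from baseline will be summarized at each scheduled time point". It adds a companion display: "For oxygen saturation an overview will be presented for the number of subjects that require supplemental oxygen". It also promises the percentage of subjects whose vital signs fall outside clinically important limits.

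SAP 4.3.4 carries this forward. It lists the parameters ("Systolic and Diastolic blood pressure, oral temperature, pulse rate, respiratory rate, arterial oxygen saturation and level of consciousness will be investigated") and the method ("Actual values and change from baseline will be summarized by treatment group at each scheduled time point"), with mean and SE "graphs over time for the actual values and changes from reference will be generated for all tests performed". It takes vital-sign abnormalities from the WHO grading scale and Appendix 3. From these it builds the worst-toxicity, treatment-emergent and shift tables.

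The plan does recognise oxygen status elsewhere. In SAP 4.2.1, Table 6 counts saturation as resolved only at 92% or more while breathing room air. Its footnote takes that condition from an item on the Vital Signs pages: "Was oxygen saturation measured on room air". SAP 4.1.2 lists supplemental oxygen at baseline (yes or no) as a baseline characteristic, so subjects both on and off oxygen are expected at entry. Protocol 9.3.4 calls for a standard pulse oximeter and does not require a room-air reading.

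Appendix 3 opens with "The following abnormalities are defined for vital signs" and then covers pulse, diastolic pressure and systolic pressure only.

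**The concern.** A saturation reading means something different on oxygen and off it. Oxygen is given because saturation is low and withdrawn when the patient recovers. A change from baseline that spans such a switch therefore tends to go against the clinical course: starting oxygen raises the reading and stopping it lowers the reading. If the arms differ in how fast subjects come off oxygen, the pooled mean change can favour the arm that is doing less well.

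The plan treats the distinction as essential for efficacy and then drops it when the same measurement is summarised for safety. One subject can count as normalised on the saturation item of Table 6 and as worse in the saturation table.

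The missing limits are a separate matter. Without them the SAP cannot deliver, for saturation or respiratory rate, a display that the protocol promises. In patients hospitalised with influenza these are two vital signs a safety reader will look for.

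**Working it through.** The documents give no saturation data, so every reading below is assumed. The scoring rules are the SAP's own: Table 6 for resolution and Table 9 for NEWS. In Table 9, saturation scores 3 at 91 or less, 2 at 92-93, 1 at 94-95 and 0 at 96 or more; any supplemental oxygen adds 2.

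**Single subjects**

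| Baseline | Later | Change | Saturation meets Table 6? | NEWS, saturation + oxygen |
|---|---|---|---|---|
| 96 on oxygen | 93 on room air | -3 | no to yes | 2 to 2 |
| 96 on oxygen | 94 on room air | -2 | no to yes | 2 to 1 |
| 90 on room air | 96 on oxygen | +6 | no to no | 3 to 2 |
| 93 on room air | 97 on oxygen | +4 | yes to no | 2 to 2 |

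In rows 1, 2 and 4 the saturation change has the opposite sign to the Table 6 result. In row 3 the subject gains 6 points by being put on oxygen.

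**One arm.** Let a share w come off oxygen (96 to 93, change -3) and the rest improve on room air (94 to 95, change +1). The mean change is -3w + (1 - w) = 1 - 4w:
- w = 10%: +0.6
- w = 25%: 0.0
- w = 30%: -0.2
- w = 50%: -1.0

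Every subject in that arm is better by construction.

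**Two arms.** Assume that 60% are on oxygen at baseline and that 70% (active) or 40% (control) of these are off it by Day 4. Saturation is 95 on oxygen, 94 after stopping and 95 if oxygen continues. The other 40% go from 93 to 95 on room air in both arms.
- Active mean change: 0.6 × [0.7 × (-1) + 0.3 × 0] + 0.4 × 2 = +0.38
- Control mean change: 0.6 × [0.4 × (-1) + 0.6 × 0] + 0.4 × 2 = +0.56
- Active minus control: -0.18
- Still on oxygen: 0.6 × 0.3 = 18% against 0.6 × 0.6 = 36%

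If the fall on stopping oxygen is d points, the difference is -0.6 × (0.7 - 0.4) × d = -0.18d. That is -0.18, -0.36 and -0.54 for d = 1, 2 and 3. The sign holds for any positive d as long as the remaining subjects behave alike in both arms.

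**The same example in NEWS points (saturation + oxygen).** Coming off oxygen goes from 3 to 1 (-2), staying on oxygen scores 0 change, and the room-air group goes from 2 to 1 (-1).
- Active: 0.6 × 0.7 × (-2) + 0.4 × (-1) = -1.24
- Control: 0.6 × 0.4 × (-2) + 0.4 × (-1) = -0.88

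Here NEWS gives the right direction, by 0.36 points.

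**The same example in three classes at Day 4.** At least 92% on room air: active 0.42 + 0.40 = 82%, control 0.24 + 0.40 = 64%. On oxygen: 18% against 36%. Below 92% on room air: none in either arm.

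**Limits.** Appendix 3 has rows for pulse and the two blood pressures. The WHO scale in SAP Appendix 2 has no item for oxygen saturation or respiratory rate. The SAP 4.3.4 abnormality tables therefore have nothing to classify these two parameters with.

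**The case against.** The strongest answer is that the reader of the safety report is not left with the saturation mean alone.
- NEWS (SAP 4.3.5) scores saturation and oxygen together at each time point and favours the active arm in the two-arm example.
- Oxygen supplementation is tabulated by visit and phase (SAP 4.1.3), and the protocol promises a count of subjects needing it. The 18% against 36% would be visible.
- The ordinal category is derived for Days 1 to 15, and it separates non-ICU inpatients on oxygen from those not on it.
- Time to improvement of vital signs and of respiratory status both require room air.

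This stands as a limit on the harm. It does not mend the saturation table, because none of these displays conditions the saturation values or changes on oxygen status. NEWS is not a full correction either. With all other items at zero, 90% on room air scores 3 on one parameter and is medium risk, while 96% on oxygen scores 2 in total and is low risk.

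A reader might infer that the plan can never show hypoxia. The documents do not support that. A saturation of 91 or less scores 3 in NEWS and so reaches at least the medium-risk category. Low saturation can also surface as an adverse event or as respiratory failure among the influenza complications. The gap is confined to the SAP 4.3.4 abnormality, worst-toxicity and shift tables.

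Two further objections hold in part. The protocol promises an overall saturation summary, so it should not be removed. A change table restricted to pairs of room-air readings drops everyone on oxygen at baseline; in the two-arm example it gives +2 against +2 and shows no difference. Finally, SAP 3.4 leaves display details to the Data Presentation Specifications, which are not among the documents reviewed, so a layout by oxygen status could be set there. The SAP text gives no sign of one.

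**Conclusion.** The point holds as a minor one, in two parts. First, the saturation values and changes are pooled over oxygen status, so the mean change is hard to interpret and can point the wrong way. Second, the promised percentage outside clinically important limits cannot be produced for saturation or respiratory rate from the limits the SAP provides.

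The size is modest and rests on assumed readings: 0.18 points against the better arm per point of fall on stopping oxygen, given 60% on oxygen at baseline and 70% against 40% coming off it. The example shows that a reversal is possible. It does not show that one is likely or large.

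A reader might go further and conclude that the trial's respiratory comparison is compromised, or that saturation is its main respiratory safety variable. The documents do not rank it so, and SAP 4.3.4 plans description only, with no between-arm test or estimate. The primary PK endpoint, the ordinal scale and the room-air time-to-event endpoints are unaffected.

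**What to change.** In SAP 4.3.4 and Appendix 3:
1. Add a three-class saturation variable: at least 92% on room air, below 92% on room air, on supplemental oxygen. Derive it from the existing room-air flag and the Table 6 limit. Show it by arm at each time point, as the worst class per phase, and cross-tabulated against baseline. State the order of the classes in advance; Table 7 already ranks non-ICU inpatients on oxygen below those not on it.
2. Add respiratory rate above 24/min, the complement of the Table 6 criterion, as an analysis category. Both limits serve tabulation only and say nothing about management.
3. Keep the overall saturation summary that the protocol promises, and also present values by oxygen status at each time point.
4. If changes are shown for pairs of readings both on room air, label them as a secondary summary of a selected subset.

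The cost is SAP wording, one derived variable and a few extra tables, with no new data.

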11.6. Efficacy Analyses

The efficacy endpoints will be analyzed on the Full Analysis Set, consisting of all subjects who were randomized, treated and had a confirmed influenza A infection, and will be analyzed by drug received.

Descriptive statistics will be used for all efficacy endpoints and will be tabulated by treatment arm and by age cohort. No formal statistical hypothesis testing will be made.

Clinical outcomes

The incidence of influenza complications will be categorized in a hierarchical fashion. The overall category will consist of any complication, consisting of the following subcategories:

- bacterial pneumonia (culture confirmed where possible),
- other bacterial superinfections,
- respiratory failure,
- pulmonary disease: asthma, chronic obstructive pulmonary disease [COPD]),
- cardiovascular and cerebrovascular disease (eg, myocardial infarction, congestive heart failure [CHF], arrhythmia, stroke),
- post-baseline ICU admission,
- all-cause mortality

The incidences on Day 28 of each (sub) category will be analyzed using logistic regression; baseline characteristics that are predictive of the incidence of complications can be included based on goodness of fit criteria. Odds ratios and associated 95% CIs will be reported of active vs. control treatment.

The time to improvement of vital signs is defined as the time from first study treatment to when at least 4 of 5 symptoms (temperature, blood oxygen saturation, heart rate, SBP, respiration rate) are recovered, including normalization of temperature and blood oxygen saturation. Normalization is defined in Table 6. If subjects satisfy these criteria at entry they will be censored at that time (effectively they will be excluded from the analysis). The data will be presented using a Kaplan-Meier curve. The time to event data will be modeled using the accelerated failure time (if the data provide an acceptable model fit) or alternatively a Cox proportional hazards model (in case the hazards are proportional). Additionally, the time to event data will be analyzed using the Gehan-Wilcoxon method.

Table 6: Resolution Criteria for Vital Signs

Assessment	Resolution Criterion
Temperature	≤ 37.2 °C or ≤ 37.8 °C rectal or tympanic
Oxygen saturation	$\geq 92\%$ on room air without supplemental oxygen
Respiration rate	≤ 24 /min
Heart rate	≤ 100 /min
Systolic blood pressure	≥ 90 mmHg

Time to improvement of respiratory status is defined as normalization of blood oxygen saturation and respiration rate. Analysis performed will be analogous to the analysis for the time to improvement of vital signs.

The ordinal scale consists of 6 categories that are exhaustive, mutually exclusive, and ordered (Table 7). For all patients, the category at Day 8 will be established as the worst category on that day. For example, if someone is discharged on Day 8, the category will be non-ICU and no supplemental oxygen (if there was no supplemental oxygen given on that day). The analysis will be performed using a proportional odds model, modeling the common odds ratio of the improvement on the ordinal scale of active treatment versus control. Baseline covariates that are predictive of the ordinal scale may be added to the model to increase the model fit. In case of missing data (>10%), a multiple imputation method under the missing-at-random assumption will be employed. Details will be provided in the Statistical Analysis Plan.

Table 7: Ordinal Scale on Day 8

Outcome
Death
Admitted to ICU or mechanically ventilated/ECMO
Non-ICU + supplemental oxygen
Non-ICU + no supplemental oxygen
Not hospitalized, but unable to continue activity
Not hospitalized and continues activities

ECMO = extracorporeal membrane oxygenation; ICU = Intensive Care Unit

Viral kinetics

Measures of viral kinetics are performed for both qRT-PCR and viral culture of nasal MT swabs:

- Duration of viral shedding defined as time to influenza A viral negativity
- Viral AUC calculated from baseline to Day 14
- Rate of decline of viral load
- Incidence of influenza A viral negativity by assessment
- Peak viral shedding titer

The time to influenza A viral negativity will be determined based on nasal MT swabs: a subject will be considered influenza A viral negative at the time point that the first negative nasal MT swab was recorded (in days). A subject will be censored at the time of the last observed non-negative swab + 1 day. The time to influenza A viral negativity will be summarized using a Kaplan-Meier curve. The accelerated failure time model will be used to compare the time to recovery for JNJ-63623872 vs. control treatment; the accelerated failure time model will use a Weibull, log-logistic, lognormal or gamma distribution based on goodness of fit criteria. Additionally, the time to event data will be analyzed using the Gehan-Wilcoxon method. The AUC will be estimated for each treatment arm using a mixed model for repeated measurements, ie, the AUC will not be calculated for each subject and then analyzed, but the AUC will be calculated for each treatment arm using the viral data over time of each subject. This approach ensures an optimal approach towards missing data. The rate of decline in quantitative viral load

will be estimated through a pre-specified linear mixed model. The incidence of viral negativity will be analyzed using logistic regression. For the peak viral shedding titer a GMR will be derived using a general linear model. For each analysis the difference between the treatment arms will be presented including the associated 95% CI. Factors that are predictive of viral titers will be included as covariates.

Patient-reported Outcomes

The time to resolution of influenza symptoms will be the time of the first of 2 evaluations (over 24 hours) in which all symptom scores for each of the 2 assessments are none or mild for the 7 primary influenza symptoms as recorded in the Flu-iiQ™ (cough, sore throat, headache, nasal stuffiness, feverishness or chills, muscle or joint pain, and fatigue).

The FLU-PRO and Flu-iiQ™ domain scores will be presented descriptively over time using descriptive statistics. A linear mixed model will be used to analyze composite symptom scores over time, per domain. For the Flu-iiQ™ a daily score will be derived averaging observed scores before the analysis. Baseline subject characteristics will be included (in particular baseline score) in case these provide to be predictive of post-baseline scores. Mean differences between treatment arms will be derived from this model using appropriate contrasts and will be presented including the associated 95% CI. For both measures, an AUC of composite symptom scores over a 7- and 14-day period per domain will be calculated and compared using a mixed model for repeated measurements.

Other PRO endpoints that will be analyzed are:

1. Time to return to usual activity and usual health (Questions 5 and 9 of the additional items for the Flu-PRO).
2. Time to significant reduction in influenza symptom severity.
3. Proportion of patients with a significant reduction (to mild or none for all influenza symptoms) at each assessment.

Other Outcomes

The length of overall hospital stay will be calculated from the date of first study drug intake up to the date of discharge. Subjects still hospitalized at the end of the study will be censored at the last contact. Data will be presented using Kaplan-Meier curves. For a comparison between treatment arms, the time to hospital discharge in days will be analyzed using an accelerated failure time model (if the data provide an acceptable model fit) or alternatively a Cox proportional hazards model (in case the hazards are proportional). Additionally, the time to event data will be analyzed using the Gehan-Wilcoxon method. The time to resumption of normal daily activities will be analyzed in an analogous fashion.

Resistance Analyses

The results of viral sequencing and phenotyping will be evaluated by the sponsor virologist. Additional exploratory characterization of the viral genotype and phenotype may be performed and will be reported accordingly.

